## **Study Protocol:**

### Purpose and Procedures:

The primary purpose of this line of research is to investigate the effects of custom carbon fiber dynamic ankle foot orthosis (CDO) design on the forces and articular contact stress at the ankle in order to reduce the development of post traumatic osteoarthritis in the ankle, which often occurs following severe ankle injury. The proposed study will provide evidence that can be used by certified prosthetists orthotists (CPOs) and physicians when choosing the CDO design with the goal of offloading the ankle and reducing contact stress.

In this research study, adult participants who have sustained a traumatic ankle fracture of the tibial pilon in the last five years will be fit with a CDO(s) with different designs. Each participant will be evaluated using a series of study measures under each of the three bracing conditions in a randomized order (CDO-A, CDO-B, CDO-C) as well as when they are not wearing any device (NoCDO). Physical performance measures will incorporate tests of agility, speed, and lower limb power to ensure that the device design changes don't negatively affect physical function. Questionnaires will be used to evaluate participants' current and desired activity level, pain with and without CDO use, satisfaction with the devices, perception of comfort and smoothness between devices, and preference between CDO designs. Semi-structured interviews will be completed to fully capture the perspective of the participant. A motion capture system will be used to evaluate walking biomechanics, allowing for comparisons between conditions, by use of computerized motion capture and force plates in the floor, as individuals walk at a self-selected and a controlled speed based on leg length. Force measuring sensors will be used to assess forces acting within the CDO. Muscle activity data will be collected using DELSYS EMG sensors. We will also complete mechanical testing of the devices and collect demographic and anthropometric data about the participant and the CDO(s).

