### Objectives and Specific Aims:

Aim 1: Determine the effect of CDO design modifications on ankle contact stress.

Aim 2: Determine the effect of CDO design modifications on physical function and gait biomechanics.

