#### Inclusion Criteria

- Between the ages of 18 and 65
- Sustained unilateral fracture of the tibial pilon within the preceding 5 years
- The fracture has completely healed
- Ability to walk 50 feet without use of an assistive device (cane, crutch, etc.)
- Ability to walk at a slow to moderate pace

- Shoe size between women's 8 and 13.5 or men's 6.5 and 13
- Ability to read and write in English and provide written informed consent
- Individuals with elevated contact stress according to model generated using standing CT images (will be answered after completing visit one)

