Patient-reported outcomes questionnaires will be used to evaluate participant physical function, activity level, pain, comfort, satisfaction, and preference in addition to multiple other relevant outcomes. The Orthotics Prosthetics Users' Survey (OPUS) is a leading measure for evaluating satisfaction with orthotic devices and services will be used to evaluate device comfort, form, and fit. Comfort and smoothness will also be assessed using a modified version of the Socket Comfort Score where comfort scores range from 0 = most uncomfortable to 10 = most comfortable, and from 0 = least smooth to 10 = most smooth. Pain will be assessed using a standard 11-point numerical pain rating scale, in which 0 = no pain and 10 = worst pain imaginable at the start of each session, and at multiple points while walking in each condition. Participants will be asked to rate the three brace designs (CDO-A, CDO-B, and CDO-C) on a standard 11-point scale, where 0 = worst imaginable device and 10 = best imaginable device, upon completion of their final testing session. The University of California, Los Angeles (UCLA) activity score is a 10-level rating scale that is used to both qualitatively and quantitatively define an individual's current and/or desired level of activity. The Patient Reported Outcomes Measurement Information System (PROMIS) will be used to evaluate physical function. Semi-structured interviews will also be used to fully capture the patients' perspectives, experience, and opinions associated with the device options they experienced as part of the study.

Ground reaction force and motion capture data will be used to evaluate the motion and loading of the lower limb and CDO devices as participants walk on an over ground walkway at self-selected speed and a controlled speed based on leg length. Retro-reflective markers will track the position and orientation of body segments and force plates imbedded in the floor will capture ground reaction forces. Muscle activity will be measured using DELSYS EMG sensors bilaterally for the soleus, tibialis anterior, medial gastrocnemius, rectus femoris, gluteus medius, biceps femoris, and vastus medialis muscles.

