Force measurement sensors will be used to measure forces acting within the CDO. For group three, Loadpad sensors (Novel GMBH, St. Paul, MN) will be placed within the proximal cuff to measure how tightly the proximal cuff is fastened. In-shoe plantar pressure distribution will be measured using the LoadSol system (Novel GMBH, St. Paul, MN) during over ground trials for all groups.

**Statistical Analysis Plan:**Analysis Methods:

The distributions of study measures will be characterized using descriptive statistics. One-way repeated measure ANOVAs will be used to evaluate the effect of CDO alignment. Paired t-tests with Bonferroni-Holm correction will be used for post-hoc comparisons.

Power Analysis:

The number of participants proposed for this study are consistent with those from prior investigations by [name] related to CDO design. Thirteen participants were sufficient to detect differences associated with AFO stiffness in a recent study by [name] (PMID: 25193884).

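### NoCDO is listed outside the randomised brace order and its test position is not stated; if that position is the same for everyone, CDO-versus-NoCDO comparisons are confounded with test order

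*Combined protocol and SAP*

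**What the plan says.** Purpose and Procedures has each participant evaluated under "three bracing conditions in a randomized order (CDO-A, CDO-B, CDO-C) as well as when they are not wearing any device (NoCDO". The count is three and the parenthesis names three braces; NoCDO follows as an addition. No other section says when NoCDO is tested.

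The same section describes measurements that set device against no device: questionnaires cover "pain with and without CDO use", and motion capture of walking is described as "allowing for comparisons between conditions". Under Design and Methods, pain is rated "at the start of each session, and at multiple points while walking in each condition", and the physical tests are the four square step test and a sit-to-stand done at maximum speed.

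Testing extends over more than one occasion. One inclusion criterion "will be answered after completing visit one", and the braces are rated "upon completion of their final testing session". There is no visit schedule.

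Both aims concern brace design; Aim 1 is to "Determine the effect of CDO design modifications on ankle contact stress". In the Statistical Analysis Plan, "One-way repeated measure ANOVAs will be used to evaluate the effect of CDO alignment", followed by paired t-tests with Bonferroni-Holm correction. No order or position term is given, and the plan does not say whether NoCDO is a level of the factor.

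**The concern.** Randomising the order protects a within-participant comparison from practice, fatigue and accumulating pain. The braces have that protection against one another. As written, NoCDO is not stated to have it against the braces. A team following the sentence literally could test every participant without a device first, or every participant last, and still comply.

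In that case a difference between a CDO and no device could be a device effect, an order effect or both. If pain rose over successive tests, NoCDO first would hide a CDO benefit and NoCDO last would create one. More participants would not help, because the bias does not depend on sample size. The pain rating at the start of each session might partly correct for build-up within a session, but the plan does not say it is used in this way, and it describes no comparable reference for the timed tests, gait or EMG.

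**Working it through.** The plan gives no figure to reproduce: there is no alpha, power, effect size, SD or drift estimate. The Power Analysis mentions 13 participants in an earlier study; 13 is used below as an assumed sample size.

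**1. Can device and order be separated?** Take a model with participant, condition and categorical position. Columns: 13 participants + 3 condition contrasts + 3 position contrasts = 19.

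- NoCDO in one fixed slot: the indicator for that slot is identical to the indicator for NoCDO, so one column is redundant. Rank is 18 of 19. CDO-A minus NoCDO is not estimable; CDO-A minus CDO-B is.
- NoCDO within a four-sequence Williams order: rank is 19 of 19, and both contrasts are estimable.

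**2. Bias of the unadjusted comparison.** Let drift be *d* per position, with NoCDO in slot *k* and the braces randomised over the other three slots. The slots sum to 10, so the mean CDO position is (10 − *k*)/3, and

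bias of (mean CDO − NoCDO) = *d* × [(10 − *k*)/3 − *k*] = *d* × (10 − 4*k*)/3.

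This gives +2*d* for slot 1, +0.67*d* for slot 2, −0.67*d* for slot 3 and −2*d* for slot 4. With *d* = 0.1, 0.25 or 0.5 residual SD, the bias is 0.2, 0.5 or 1.0 SD in an end slot and 0.07, 0.17 or 0.33 SD in a middle slot. The brace-versus-brace bias is zero.

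**3. Effect on the planned tests.** This was simulated with residual SD 1, *n* = 13, no true effect, NoCDO treated as a fourth ANOVA level, post-hoc paired t-tests only after a significant ANOVA, and Holm over the six pairs at a 5% level. The table gives the probability of at least one false result among the three CDO-versus-NoCDO contrasts.

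| NoCDO position | *d* = 0.1 | *d* = 0.25 | *d* = 0.5 |
|---|---|---|---|
| First or last | about 3% | about 12% | about 52% |
| Second or third | about 2% | about 2% | 4 to 5% |
| Randomised | about 1.5% | about 1.5% | about 1.5% |

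The rate is also about 1.5% when there is no drift.

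**4. Could a model repair it afterwards?** Without a position term, the standard error of CDO-A minus NoCDO is √(2/13) = 0.392 residual SD. Adding a linear position term makes the contrast estimable, with these standard errors:

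- NoCDO first: 0.545 (0.545/0.392 = 1.39)
- NoCDO last: 0.566 (0.566/0.392 = 1.44)
- NoCDO second: 0.398, almost free

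The repair is right only if drift is linear through NoCDO's own slot. If only the first test is shifted, by 0.5 SD, and NoCDO is first, the linear term leaves the whole 0.5 SD bias in place. With a Williams order, a position term gives a standard error of 0.393 and needs no assumed shape.

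**The case against.** The strongest reply is that the harm is hypothetical. The slot is unstated, not shown to be fixed, and the sentence does not exclude randomising all four conditions. A reader might infer that NoCDO is in fact tested in one set position; the documents do not support that, and the point must remain conditional.

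Second, no formal CDO-versus-NoCDO test is named. The aims concern brace design, the ANOVA factor is alignment, and NoCDO has no alignment; on that reading, such comparisons may already be descriptive. This has force, and it is why the point does not reach the aims. A reader might infer that the study's main results are compromised; they are not. But the plan collects pain with and without a device and expects comparisons between conditions in gait, and it does not say that NoCDO is outside the ANOVA factor.

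Third, error rates can be made to look worse than the planned procedure allows. A single uncorrected paired t-test with NoCDO in an end slot gives about 8%, 21% and 61% for the three drift sizes. The plan specifies Holm after ANOVA, and the corresponding rate per contrast is about 1%, 5% and 30 to 31%. The uncorrected rates should not be attributed to this plan. Holm lowers the rates but leaves the bias unchanged.

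Fourth, the drift sizes have no basis in the documents. Practice and fatigue may offset each other, and fatigue need not carry over between visits. This is correct: the net effect may be small. Drift across the other three slots could also be estimated from the braces, so only its extension to NoCDO's slot has to be assumed.

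**Conclusion.** The concern holds in conditional form. The stated scheme randomises the three braces and leaves NoCDO's position open. If that position is the same for all participants, CDO-versus-NoCDO differences are completely aliased with an unrestricted position effect, and the planned analysis cannot separate them. This part is structural and does not depend on the assumed figures.

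The size does depend on them. Under linear drift, the bias is twice the per-position drift for an end slot and two thirds of it for a middle slot. The error rates also rest on the assumed 13 participants and on NoCDO being a fourth ANOVA level. An end slot with large drift does real damage; a middle slot or small drift does little under the planned correction. Treating CDO-versus-NoCDO as secondary is an inference from the aims, since the documents set no hierarchy of outcomes. The change is worth making because it is cheap before testing starts, whereas afterwards the order effect can be removed only by assuming its shape.

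**What to change.** Include NoCDO in one randomised or counterbalanced order of all four conditions, for example a four-sequence Williams square allocated in blocks, and say so in Purpose and Procedures. A position term in the model is optional and costs almost no precision (standard error 0.393 against 0.392 residual SD at *n* = 13). It is useful when the number of participants is not a multiple of four, as with 13, because the square is then not exactly balanced.

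The cost is a new order list, one protocol sentence and, if wanted, one model term. The downside is less convenient session flow. If NoCDO testing is meant to come before CDO fitting, it would have to move to a later session.

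If NoCDO must keep a fixed slot, state the slot, report CDO-versus-NoCDO contrasts as descriptive, and say in the Statistical Analysis Plan that NoCDO is not a level of the ANOVA factor. This changes only wording, at the price of a weaker claim about CDO against no device.

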### Objectives and Specific Aims:

Aim 1: Determine the effect of CDO design modifications on ankle contact stress.

Aim 2: Determine the effect of CDO design modifications on physical function and gait biomechanics.

### Background and Significance:

Post-traumatic osteo-arthritis (PTOA) is a significant problem caused by chronic, increased, contact stress and fracture severity. Surgical fracture reduction has been the mainstay of intra-articular fracture (IAF) treatment for decades, but it is not the only factor influencing joint contact stresses. Furthermore, even with the best surgical effort, there often remains residual incongruity that leads to elevated contact stress. Recent advances in bracing provide an attractive complementary treatment solution. CDOs have been used to dramatically improve function and reduce pain in hundreds of service members with traumatic limb injury [6-10]. CDOs are comprised of a proximal cuff sitting just below the knee, a posterior strut used to store and return energy, a semi-rigid foot plate, and a heel cushion between the footplate and shoe [11]. These components can be varied to influence the forces and motions experienced by the limb [11-14], which in turn influence the forces on the foot and the activation of muscles that cross the ankle [8, 15, 16]. Recent findings indicate that this can decrease load transfer across the ankle, which implies that CDOs may be able to be effectively tuned to reduce articular contact stress.

### Inclusion/Exclusion Criteria:

Tibial pilon fracture participants:

#### Inclusion Criteria

- Between the ages of 18 and 65
- Sustained unilateral fracture of the tibial pilon within the preceding 5 years
- The fracture has completely healed
- Ability to walk 50 feet without use of an assistive device (cane, crutch, etc.)
- Ability to walk at a slow to moderate pace

- Shoe size between women's 8 and 13.5 or men's 6.5 and 13
- Ability to read and write in English and provide written informed consent
- Individuals with elevated contact stress according to model generated using standing CT images (will be answered after completing visit one)

#### Exclusion Criteria

- Pain > 6/10 while walking
- Increase in pain during testing of 3/10 or greater
- Neurologic, musculoskeletal (including bilateral fractures) or other condition limiting function of the contralateral extremity
- Medical or psychological condition that would preclude functional testing (ex. moderate or severe brain injury, stroke, heart disease)
- Wounds to the calf that would prevent CDO fitting
- Fractures secondary to neuropathy or severe osteopenia
- Classification as non-ambulatory
- Previous fractures near the tibial pilon on the involved limb
- Surgery on involved limb anticipated in the next 6 months
- Requirement of a knee stabilizing device (i.e. KAFO, KO...) to perform daily activities
- Visual or hearing impairments that limit walking ability or limit the ability to comply with instructions given during testing
- BMI greater than 40
- Pregnancy

#### Healthy able-bodied participants:

##### Inclusion Criteria

- Between the ages of 18 and 65
- Shoe size between women's 8 and 13.5 or men's 6.5 and 13
- Healthy individuals without a current complaint of lower extremity pain, spine pain, or medical or neuromusculoskeletal disorders that have limited participation in work or exercise in the last 6 months
- Full active range of motion of the bilateral lower extremities and spine
- Ability to hop without pain
- Ability to perform a full squat without pain
- Ability to read and write in English and provide written informed consent

##### Exclusion Criteria

- Diagnosed moderate or severe brain injury
- Prior lower extremity injury resulting in surgery or limiting function for greater than 6 weeks
- Diagnosis of a physical or psychological condition that would preclude testing (e.g. cardiac condition, clotting disorder, pulmonary condition)
- Visual or hearing impairment that would interfere with instructions given during testing

- Require an assistive device
- Wounds to the foot or calf that would prevent CDO use
- BMI greater than 40
- Pregnancy

### Design and Methods:

Personal/demographic and anthropometric information will be used to fully characterize the study participants (race, ethnicity, education, date and mechanism of injury, injury characteristics, surgical history, current device (if any), age, biological sex, study limb (left or right), height, weight, leg length, shoe type, shoe length and width).

Physical performance measures provide an objective and responsive assessment of an individual's functional mobility. The four square step test (4SST) is a standardized and widely used test of balance and agility where a 1-inch pipe is placed on the floor in the shape of a Maltese cross. The patient is instructed to begin in the back-left quadrant then to move 1) forward, 2) sideways right, 3) backward, then 4) sideways left, then to move in the reverse direction back to the original quadrant. The sit to stand 5 times (STS5) test is a well-established measure of lower limb muscle strength, endurance, and mobility where patients are instructed to start the test sitting with their arms folded across their chest and with their back against a standard chair. Patients are then instructed to stand up and sit down 5 times as fast as possible, avoiding touching their back to the chair during each repetition.

Patient-reported outcomes questionnaires will be used to evaluate participant physical function, activity level, pain, comfort, satisfaction, and preference in addition to multiple other relevant outcomes. The Orthotics Prosthetics Users' Survey (OPUS) is a leading measure for evaluating satisfaction with orthotic devices and services will be used to evaluate device comfort, form, and fit. Comfort and smoothness will also be assessed using a modified version of the Socket Comfort Score where comfort scores range from 0 = most uncomfortable to 10 = most comfortable, and from 0 = least smooth to 10 = most smooth. Pain will be assessed using a standard 11-point numerical pain rating scale, in which 0 = no pain and 10 = worst pain imaginable at the start of each session, and at multiple points while walking in each condition. Participants will be asked to rate the three brace designs (CDO-A, CDO-B, and CDO-C) on a standard 11-point scale, where 0 = worst imaginable device and 10 = best imaginable device, upon completion of their final testing session. The University of California, Los Angeles (UCLA) activity score is a 10-level rating scale that is used to both qualitatively and quantitatively define an individual's current and/or desired level of activity. The Patient Reported Outcomes Measurement Information System (PROMIS) will be used to evaluate physical function. Semi-structured interviews will also be used to fully capture the patients' perspectives, experience, and opinions associated with the device options they experienced as part of the study.

Ground reaction force and motion capture data will be used to evaluate the motion and loading of the lower limb and CDO devices as participants walk on an over ground walkway at self-selected speed and a controlled speed based on leg length. Retro-reflective markers will track the position and orientation of body segments and force plates imbedded in the floor will capture ground reaction forces. Muscle activity will be measured using DELSYS EMG sensors bilaterally for the soleus, tibialis anterior, medial gastrocnemius, rectus femoris, gluteus medius, biceps femoris, and vastus medialis muscles.

Force measurement sensors will be used to measure forces acting within the CDO. For group three, Loadpad sensors (Novel GMBH, St. Paul, MN) will be placed within the proximal cuff to measure how tightly the proximal cuff is fastened. In-shoe plantar pressure distribution will be measured using the LoadSol system (Novel GMBH, St. Paul, MN) during over ground trials for all groups.

**Statistical Analysis Plan:**Analysis Methods:

The distributions of study measures will be characterized using descriptive statistics. One-way repeated measure ANOVAs will be used to evaluate the effect of CDO alignment. Paired t-tests with Bonferroni-Holm correction will be used for post-hoc comparisons.

Power Analysis:

The number of participants proposed for this study are consistent with those from prior investigations by [name] related to CDO design. Thirteen participants were sufficient to detect differences associated with AFO stiffness in a recent study by [name] (PMID: 25193884).

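### Does the ANOVA factor CDO alignment, whose levels are not listed, leave the brace analysis undefined?

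*Combined protocol and SAP*

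**What the plan says.** The inferential plan is two sentences under Analysis Methods. The first reads "One-way repeated measure ANOVAs will be used to evaluate the effect of CDO alignment". The second assigns paired t-tests with a Bonferroni-Holm correction to the post-hoc comparisons. It gives no pairs, no alpha and no analysis group.

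The rest of the document supplies the context:

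- **Conditions.** Purpose and Procedures has each participant tested in three braces in randomised order and also without a device: "CDO-A, CDO-B, CDO-C) as well as when they are not wearing any device (NoCDO". It adds: "A motion capture system will be used to evaluate walking biomechanics, allowing for comparisons between conditions".
- **Aims.** Aim 1 is "Determine the effect of CDO design modifications on ankle contact stress" and Aim 2 is "Determine the effect of CDO design modifications on physical function and gait biomechanics".
- **Ratings.** Design and Methods says: "Participants will be asked to rate the three brace designs (CDO-A, CDO-B, and CDO-C", with no rating for the no-device condition.
- **Groups.** Purpose and Procedures says that "adult participants who have sustained a traumatic ankle fracture of the tibial pilon in the last five years will be fit with a CDO(s". The eligibility section also has a list for "Healthy able-bodied participants", and the force-sensor paragraph mentions a group three and all groups.

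**The concern.** The plan has one omnibus test, and the name of its factor matches nothing else in the study description. Alignment appears elsewhere only in the title of a cited reference. The aims speak of design, and Background and Significance names the cuff, strut, foot plate and heel cushion as the parts that can be varied. CDO-A, CDO-B and CDO-C are not defined further.

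Because all four conditions are measured, a reader could take the factor to have four levels. The F-test could then be significant only because wearing any brace differs from wearing none, and still be reported as an effect of alignment. The number of post-hoc pairs, and so the strictness of the Holm correction, would also change. If the choice were made after seeing the data, the plan would seem to leave room for a favourable one. It is also not stated whether able-bodied participants enter these analyses.

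**Working it through.** **1. Which reading does the text support?**

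| Source | Three levels | Four levels |
|---|---|---|
| Analysis Methods | The factor is a property of the device; NoCDO has no device and so no value of it | – |
| Purpose and Procedures | The three bracing conditions are named as a set, with NoCDO added separately | All four are measured; motion capture allows comparisons between conditions |
| Aims 1 and 2 | Both ask about changes in brace design | – |
| Design and Methods | The three brace designs are rated as a set | – |

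The only support for four levels is that NoCDO is measured, plus a sentence describing what motion capture makes possible, not what the ANOVA tests. Whether the braces differ in alignment or the word is a loose label for design, the levels are CDO-A, CDO-B and CDO-C.

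**2. What depends on the reading?** Pairs = k(k−1)/2; first Holm threshold = 0.05/pairs. The 0.05, two-sided, is an assumption.

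- k = 3: 3×2/2 = 3 pairs; 0.05/3 = 0.0167.
- k = 4: 4×3/2 = 6 pairs; 0.05/6 = 0.0083.

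Once the levels are fixed, the pairs follow. This is one ambiguity, not two.

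**3. Are brace conclusions valid either way?** Suppose the braces are identical and NoCDO differs, so that exactly three brace pairs are true nulls. Before the first false rejection, Holm can have rejected at most the three NoCDO pairs, so its divisor is still at least 3. The chance of a false brace claim is therefore at most 3 × 0.05/3 = 0.05, with three pairs or six.

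Simulation agrees. Assumed inputs, none given in the documents for this trial: n = 13 (the earlier stiffness study's size, from Power Analysis), equal variances, and (brace–brace, brace–NoCDO) correlations of (0.8, 0.7), (0.9, 0.6) and (0.95, 0.5). With NoCDO 0.4 to 0.8 SD away, a false brace pair is declared in 4.4%-4.7% (three pairs) or 2.5%-3.7% (six pairs).

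**4. Can choosing late inflate brace claims?** In the six-pair family, each brace pair is multiplied by the number of hypotheses not yet rejected. That number is never smaller than in the three-pair family. So every brace pair significant among six is also significant among three. Switching readings cannot add a brace claim beyond the three-pair set, which is itself held at 5%.

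**5. What does change?**

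- *Omnibus F.* Identical braces, NoCDO 0.6 SD away: the three-level F is significant in 5%/5%/5% at the three correlation points, the uncorrected four-level F in 81%/74%/67%. The latter are not false positives, because NoCDO truly differs. Only the label would mislead.
- *Power.* At n = 13, the standardised paired difference detectable with 80% power at the first Holm step is 1.02 (three pairs) or 1.13 (six). For an assumed difference of 1.0, power is 78% or 67%.

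The 13 in Power Analysis cannot be rederived, as no effect size, SD, alpha or power accompanies it. It serves here only as an illustrative n.

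**6. What would a fuller rewrite gain?** Putting brace pairs and NoCDO pairs in separate Holm families raises the null chance of any false positive to 7.0%-8.1%, against 3.7%-4.4% for one six-pair family. That is a trade-off, not a correction. A Greenhouse-Geisser adjustment concerns sphericity, a separate question. With three levels and equal brace correlations, the unadjusted F is already at 4.9%-5.2%.

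**The case for a change.** The strongest case for a change is that an analysis plan should not need inference. All four conditions are recorded, the plan never says how NoCDO enters, and naming the levels would cost one phrase. The four-level reading could also hide what the aims seek. With one brace 0.4 SD below the other two and NoCDO, under the same assumed inputs, the three-level F is significant in 59%/89%/99.6% and the uncorrected four-level F in 49%/50%/45%. At least one true brace difference is found in 51%/83%/98.8% with three Holm pairs, against 39%/73%/97% with six.

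What stands is that the wording is loose and that listing the levels would help a reader. The losses shown arise only under the reading with less support in the text. They are losses of power, not of validity, and their size rests on correlations and shifts that the documents do not give.

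The point about groups is weaker still. A one-way within-participant ANOVA makes no between-group comparison, the bracing conditions are assigned to the fracture participants, and the group references occur in sentences about sensors. Part of the document was not available, so it cannot be said that the groups are nowhere defined.

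**Conclusion.** No change to the plan is needed. The factor is named loosely and its levels are not listed, but the surrounding text points to one reading: three braces, three pairs. Under that reading, repeated-measures ANOVA with Holm-corrected paired t-tests answers both aims. If an analyst added NoCDO as a fourth level, the omnibus F would answer a broader question and the strictest Holm step would move from 0.0167 to 0.0083, yet the error rate for brace comparisons would stay at or below 5%.

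That bound comes from the Holm procedure itself and needs only valid paired tests. The power figures assume a two-sided 0.05 level and 13 participants, and the simulated rates also assume the stated correlations and shifts. They illustrate direction and do not describe this trial.

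### Free improvement, not an error: for the three CDO pairs, Holm's middle cut-off guards against an impossible configuration, and Shaffer's step-down version recovers some power at the same 5% family-wise level

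*Combined protocol and SAP*

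**What the plan says.** Under Analysis Methods, the SAP sets an omnibus test, "One-way repeated measure ANOVAs will be used to evaluate the effect of CDO alignment", and then the pairwise step: "Paired t-tests with Bonferroni-Holm correction will be used for post-hoc comparisons". It does not say whether the pairs are tested only after a significant ANOVA, which pairs form the family, what alpha applies, or how sphericity is handled.

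Purpose and Procedures has each participant measured under "three bracing conditions in a randomized order (CDO-A, CDO-B, CDO-C) as well as when they are not wearing any device (NoCDO". The family could therefore be the three device pairs or all six pairs.

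Power Analysis gives no calculation. It says "The number of participants proposed for this study are consistent with those from prior investigations" and adds "Thirteen participants were sufficient to detect differences associated with AFO stiffness in a recent study". Thirteen is the size of a cited earlier study. The text available states no planned N.

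**The concern.** Both specific aims ask about the effect of CDO design modifications, so the device-against-device comparisons carry the trial's answer. Holm tests the three ordered p-values at 0.05/3, 0.05/2 and 0.05. The second step is set as if two of the three equalities could still hold after one has been rejected. Among three means that cannot happen.

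In a small within-subject study, the unnecessary strictness at this step costs some chance of separating one design from both others, which is the result a clinician choosing among designs would need.

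**Working it through.** **Inputs.** From the documents: paired t-tests, Holm correction, three devices plus NoCDO. There is no power figure in the plan to reproduce. Assumed, because the documents do not state them: family-wise alpha 0.05, two-sided, per outcome; n = 13, with 20 and 30 as a range; equal variances and correlations; no dropout; A = B, with C differing from both by dz (mean paired difference divided by its SD) of 0.5 to 1.2.

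**Why 3, 1, 1 is enough.** Take the number of pairwise equalities that are true.
- All three true: a false rejection must begin with the smallest p-value at or below 0.05/3 = 0.0167. By Bonferroni, the chance is at most 3 × 0.05/3 = 0.05.
- Exactly two true: impossible, since A = B and B = C imply A = C.
- Exactly one true: that pair is never tested at a cut-off above 0.05.

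Family-wise error is therefore at most 5% in every possible case. Each paired t-test uses the variance of its own differences, so sphericity is not needed.

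**Where the two procedures differ.** The first and third cut-offs are the same. They differ only when the smallest p-value is at most 0.0167 and the second lies above 0.05/2 = 0.025 but not above 0.05. Every Shaffer cut-off is at least as large as Holm's, so no Holm rejection is lost.

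**Size at n = 13, dz = 0.8** (40,000 simulated trials; the standard error of a proportion is at most √(0.25/40,000) = 0.25 points):

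| Measure | Holm | Shaffer 3, 1, 1 | Gain (points) |
|---|---|---|---|
| At least one true pair | 73.2% | 73.3% | 0.1 |
| Both true pairs | 46.4% | 57.4% | 11.0 |
| Average per true pair | 59.8% | 65.3% | 5.5 |
| Family-wise error | about 3.1% | about 4.5% | – |

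Consistency check: with two true pairs, per-pair power is the mean of the first two rows. For Holm, (73.2 + 46.4)/2 = 59.8. For Shaffer, (73.3 + 57.4)/2 = 65.35. Both agree with the third row.

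**Range over dz 0.5 to 1.2 at n = 13.** The per-pair gain is 2.3 to 5.5 points, and the gain for at least one pair is at most 0.2. The both-pairs gain is twice the per-pair gain minus the at-least-one gain: about 2 × 2.3 − 0.2 = 4.4 at the low end and 2 × 5.5 − 0.1 = 10.9 at the high end.

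**Range over n at dz = 0.8.** The both-pairs gain falls to about 7 points at n = 20 and 2 at n = 30.

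**Another pattern.** With evenly spaced devices and a largest gap of 0.8 at n = 13, the gain is 4.3 points per pair. All three pairs are found in 2.5% versus 3.0% of trials, and at least one in 60.2% under both.

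**Error when all three devices are equal.** Ungated Holm and Shaffer have the same family-wise error, about 4.6%. Under a strongly non-spherical null (variances 0.1, 0.1, 1.5), Shaffer stays at about 4.0%.

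**Six pairs with NoCDO.** The number of true equalities can only be 6, 3, 2, 1 or 0, so the multipliers become 6, 3, 3, 3, 2, 1 instead of 6, 5, 4, 3, 2, 1. With one condition differing by dz 1.0, finding all three true pairs rises from 49.9% to 56.5%. If NoCDO is far from every device, its three pairs are rejected first and use up 6, 3, 3. The remaining 3, 2, 1 are Holm's own multipliers. With one CDO then differing by 0.8, all true pairs are found in 46.4% of trials under both methods.

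**The case against.** The main objection is that nothing is broken. Holm on paired t-tests is standard and controls family-wise error strongly whatever the family or covariance; Shaffer's version is less familiar. That stands, and it is why this is an efficiency point only.

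Several stronger readings are tempting, and the documents do not support them.
- *The trial loses about 10 points of power.* That size fits only finding both true pairs, with one device differing, near n = 13. No planned N, effect size or alpha is stated, and 13 is a precedent.
- *The correction is paid twice, through the ANOVA and again through Holm.* The SAP writes no gate; the term post-hoc only suggests one. At n = 13 and dz 0.8, an implied gate costs about 1 point per pair and nothing for finding both.
- *Holm's strictness buys nothing.* Realised error does rise, from about 3.1% to 4.5% at dz 0.8. The extra power comes from using more of the permitted 5%.
- *Every pair could be tested at full alpha after a significant ANOVA.* With four conditions this gives a family-wise error of 12.6% when one condition differs. With three conditions, strong non-sphericity and an uncorrected F, it gives 6.3%. Holm does protect in those settings.

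The objection that the benefit vanishes if NoCDO shares the family and is well separated from the devices also stands. It determines the form of the fix.

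**Conclusion.** The planned correction is valid but stricter than three conditions require. For a family of exactly the three CDO pairs, Shaffer's step-down version is never less powerful than Holm, stays within the same 5% level and needs no sphericity assumption.

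The validity argument is exact. The sizes are conditional on the assumed n = 13, two-sided 0.05 and one device differing by dz 0.5 to 1.2: a modest gain per pair, a larger one for separating one design from both others, and essentially none for detecting that some pair differs. The gain shrinks as n grows. All figures are per outcome; multiplicity across outcomes is a separate matter.

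**What to change.** Amend the pairwise sentence under Analysis Methods, before outcome data are seen, to state that:
- the three CDO pairs form their own family at two-sided 0.05 (or whatever alpha the sponsor sets);
- paired t-tests use Shaffer's step-down version of Holm, with ordered p-values multiplied by 3, 1, 1, stopping at the first non-significant result;
- a significant omnibus F is not required before the pairs are tested.

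If the NoCDO pairs are to share the family, use 6, 3, 3, 3, 2, 1 and accept that this gains nothing when NoCDO differs greatly from every device. If they are kept apart, say so, because the 5% level then applies to each family separately.

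The cost is one SAP sentence and one changed line of analysis code. It needs no extra participants, visits or data.
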